21-22	Prior to evening dose and serial sampling at 1, 2, 4, 6, 8, 12, 14, 16, 18, and 24 hours after evening dose application.	Prior to evening dose and serial samples at 1, 2, 4, 6, 8, 12, 14, 16, 18 and 24 hours post dose application.	Sparse ¹ sampling as per sampling design in Table 3	Sparse ¹ sampling as per sampling design in Table 3
-------	--	---	--	--

1 The sparse blood sampling schedule for Part B (pediatrics) has been decided after generation of PK profiles in adults in Part A. The schedule consists of two sets: Set 1 with sampling time points of 0, 2, and 8 hours and Set 2 with sampling time points of 4, 12, 18, and 24 hours. Half of the subjects will follow Set 1 and other half will follow Set 2 and this assignment will be in a serial order based on the sequence of randomization for test and reference treatments across the sites. The assignment of sets will cross over between the Day 14 and Day 21, such that each subject will provide a total of 8 PK samples including Day 1 pre-dose as presented in the table below.

Table 3: Sparse Blood Sample Collection for Pharmacokinetic Analysis

Sparse sampling schedule	Day 1	Time Points in Hours (Post evening dose: Day 14 and Day 21)						
		Day 14-15			Day 21-22			
		Set 1	0 (Pre-dose)	0 (Pre-dose)	2	8	4	12
Set 2	0 (Pre-dose)	4	12	18	24	0 (Pre-dose)	2	8

TABLE OF CONTENTS

COMPLIANCE STATEMENT.....2

SIGNATURES.....2

GENERAL INFORMATION4

SYNOPSIS5

TABLE OF CONTENTS17

LIST OF TABLES19

LIST OF ABBREVIATIONS20

LIST OF DEFINITIONS21

1 INTRODUCTION.....22

2 ETHICAL CONSIDERATIONS.....22

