11.2.2 Pharmacokinetic Analysis Population

Samples from all subjects who provide evaluable data will be assayed; these subjects will be included in the PK and statistical analysis. In order to be considered evaluable, a subject must have PK samples collected on both Day 14 and Day 21. An unequal number of subjects per arm will be used.

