11.4 Pharmacokinetic Analyses

Tazarotene and tazarotenic acid plasma concentrations produced by the application of the study products will be determined to establish the PK profile of each treatment regimen. Below limit of quantitation concentrations (coded BLQ) will be treated as zero for all statistical analyses. The PK parameters will be derived from the plasma concentrations versus time profiles. All reported sampling time deviations following application for test and Reference will be taken into consideration for evaluation of PK parameters.

In the case where concentrations of tazarotene and tazarotenic acid cannot be determined due to bioanalytical or clinical reasons, these values will be set to missing for the PK and statistical analysis.

In the case where less than 3 consecutive measurable concentrations of tazarotene and tazarotenic acid are observed, the area under the curve (AUC) parameters will not be estimated for that specific study period.

The following PK parameters will be calculated for tazarotene and tazarotenic acid on Day 14 and Day 21 using a noncompartmental approach. The linear trapezoidal rule will be used to estimate the AUC.

$C_{\max(ss)}$:	Maximum observed maximum plasma concentration during a dosing interval at steady state
$AUC_{0-12(ss)}$	Area under the concentration–time curve from time zero to 12 hours post-dose, at steady state
$AUC_{0-24(ss)}$	Area under the concentration–time curve from time zero to 24 hours post-dose, at steady state
$T_{\max(ss)}$	Time to reach observed maximum plasma concentration, at steady state
$C_{\min(ss)}$	Minimum observed plasma concentration during a dosing interval at steady state

The absorption and disposition parameters will be determined using a noncompartmental approach, the trapezoidal rule will be used to estimate the area under the curve. The PK parameters of interest for this study will be:

Day 14 and Day 21: $T_{\max(ss)}$, $C_{\max(ss)}$, $AUC_{0-12(ss)}$, $AUC_{0-24(ss)}$, $C_{\min(ss)}$,

For Part B, plasma concentration data generated from sparse samples (maximum 4 time points from each subject) on Day 14 and Day 21 will be used for calculation of PK parameters: $C_{\max(ss)}$, $AUC_{(ss)}$, $C_{\min(ss)}$.

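### The AUC analysis in Section 11.4 does not fit the Part B sampling: no child has a same-day AUC0-12 or AUC0-24, and no sparse-data method is named

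*Combined protocol and SAP*

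**What the plan says.** Footnote 1 to Table 2 fixes two sampling schedules for Part B. The shorter is "Set 1 with sampling time points of 0, 2, and 8 hours". The longer, which has one more sample, is "Set 2 with sampling time points of 4, 12, 18, and 24 hours". On each PK day the children are split equally between the two, and "The assignment of sets will cross over between the Day 14 and Day 21". (The Set 1 row of Table 3 is cut off in the supplied text; the footnote gives both sets in full.)

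On methods, Section 11.4 states that "The following PK parameters will be calculated for tazarotene and tazarotenic acid on Day 14 and Day 21 using a noncompartmental approach", with the linear trapezoidal rule for AUC. It defines AUC0-12(ss) and AUC0-24(ss). Part B then has its own shorter list, in which the area is written AUC(ss) with no interval: "plasma concentration data generated from sparse samples (maximum 4 time points from each subject) on Day 14 and Day 21 will be used".

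Two data rules follow. One is "Below limit of quantitation concentrations (coded BLQ) will be treated as zero for all statistical analyses". The other withholds the AUC: "In the case where less than 3 consecutive measurable concentrations of tazarotene and tazarotenic acid are observed", no area is estimated for that period.

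Inference on all PK parameters is by a parametric ANOVA, with 90% confidence intervals for ratios of geometric means. Section 11.4 names AUC0-24(ss) in that sentence. The synopsis has the same sentence with AUC(ss), for Day 14 and Day 21. Neither sets Part B apart. Section 11.2.2 adds: "In order to be considered evaluable, a subject must have PK samples collected on both Day 14 and Day 21". Sections 11 and 11.4 refer to a separate statistical plan that is not in the supplied text.

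**The concern.** An ANOVA of ln-transformed AUC needs one AUC per subject, and the stated trapezoid is calculated by day. Part B sampling cannot supply that for any standard interval. Whoever runs the analysis must choose a route that the plan does not name: leave out the paediatric AUC, report whatever span was sampled, join a child's two days, or pool children. These routes estimate different quantities.

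Part B is up to 38 of about 62 subjects and the only evidence below age 17 on the primary objective. Its sampling schedule is already decided, so the matching estimator can be fixed now. In an open-label study it is better fixed before the paediatric concentrations are seen.

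**Working it through.** **1. The plan's own counts reproduce.** Samples per Part B child: 1 (Day 1) + 3 (Set 1) + 4 (Set 2) = 8, as Table 2 footnote 1 states. Enrolment: 24 + 38 = 62, and 26 + 12 = 38.

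**2. Same-day coverage.**

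| Set | Times (h) | Span | Share of 24 h |
|---|---|---|---|
| 1 | 0, 2, 8 | 8 h | 8/24 = 33% |
| 2 | 4, 12, 18, 24 | 20 h | 20/24 = 83% |

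Set 1 stops before 12 hours and Set 2 has no time-zero value. The number of children with same-day data across 0-12 or 0-24 hours is therefore 0. With 26 Test and 12 Reference enrolled, each PK day has 13 + 6 children on each set.

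**3. If the trapezoid is run over the sampled times.** On a flat profile the two areas are 33% and 83% of AUC0-24, with geometric mean sqrt(0.333 x 0.833) = 0.53. The two-set mixture adds an ln-scale SD of ln(20/8)/2 = 0.458.

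The documents give no CV, so 50% is an assumption: SD = sqrt(ln(1 + 0.5^2)) = 0.472, which becomes sqrt(0.472^2 + 0.458^2) = 0.658. The 90% interval factor is exp(t x SD x sqrt(1/n1 + 1/n2)):

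- 16 vs 12 (t = 1.706): 1.36 becomes 1.54.
- 26 vs 12 (t = 1.688): 1.32 becomes 1.47.

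The 16 vs 12 case pairs the minimum number of evaluable Test children with all enrolled Reference children.

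**4. Effect on the ratio.** The assumed profiles are one-compartment at steady state, Test every 12 hours and Reference every 24 hours, ka 0.3/h. With a half-life of 6 hours the shares of AUC0-24 are 0.337 and 0.766 for Test, and 0.423 and 0.776 for Reference. The geometric means are 0.508 and 0.573, and their ratio is 0.887. The 11-point Part A grid recovers 0.991 (Test) and 0.997 (Reference), so relative to that grid the ratio is 0.887/(0.991/0.997) = 0.89. With a half-life of 18 hours the same steps give about 0.97. The ratio is thus 3% to 11% low when sets are balanced within arms.

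**5. The three-concentration rule.** A Set 1 day has exactly three samples, so one non-measurable value voids its AUC. If each sample is independently below the limit with probability p (an assumption), the loss is:

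- Set 1, 1 - (1-p)^3: 27% of child-days at p = 10% and 49% at p = 20%.
- Set 2, 1 - [(1-p)^4 + 2p(1-p)^3]: 20% and 39%.

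Correlation within a child lowers these. At a correlation of 0.6 they are 16-30% and 14-28%.

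**6. What the design can deliver.** Pooled within arm and day, the times are 0, 2, 4, 8, 12, 18 and 24 hours. The trapezoid weights are 1, 2, 3, 4, 5, 6 and 3 hours, which sum to 24. Set 1 times carry 1 + 2 + 4 = 7 and Set 2 times carry 3 + 5 + 6 + 3 = 17. Over assumed profiles with ka 0.15 to 1.0/h and half-life 6 to 18 hours, this grid recovers 94% to 99.5% of AUC0-24.

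**The case against.** A reader might infer that Part B AUC has no interval and that the design offers no workable method. The documents do not support either.

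- **Interval.** Section 4 uses AUC(ss) for the whole study, and the same confidence-interval sentence has AUC(ss) in the synopsis and AUC0-24(ss) in Section 11.4. The label is probably shorthand for AUC0-24(ss). It needs confirming, but that answers only the interval and not the method.
- **Method.** The two sets interleave well, and Section 11.4 already plans mean profiles at theoretical times. Those are for presentation, however. No sentence links them to an AUC, and no variance method is given.

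It is also fair to say that the Part B sentence never states that areas are per subject. That reading comes from the ANOVA and the three-concentration rule.

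Other rescues are possible but unwritten. Using the 24-hour value for time zero would give Set 2 children an AUC0-24 (92% to 98% of the true value on the assumed profiles) but does nothing for Set 1. Joining a child's two days is neither stated nor excluded. The crossover and the both-days rule would permit it, but the result would not be by day. For Test it would also mix samples after a rinsed Day 15 morning application with samples after the unrinsed Day 22 one.

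On harm, no passage directs that unequal spans be reported as one AUC, and an ANOVA term for sampling set would absorb most of the added SD. No formal adult-paediatric comparison is specified, so none is counted as at stake. Section 11.1 says that the study does not aim at bioequivalence. The separate SAP may already resolve the point. All of this limits the size of the problem. The mismatch between the written analysis and the written sampling remains.

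**Conclusion.** The point holds as a mismatch between analysis and sampling, of minor to moderate severity. From the documents alone, no Part B child can have a same-day AUC0-12 or AUC0-24, and the stated trapezoid, three-concentration rule and ANOVA make no allowance for that. Applied per child, they give no paediatric AUC0-24 or combine 8-hour and 20-hour areas.

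The figures beyond the coverage count rest on assumed profiles, CV and below-limit rates, and matter only if unequal spans are actually analysed as one variable. Even then the interval errs on the wide side and the Test/Reference bias is modest. A reader should not conclude that the paediatric data are unusable or that the ratio would be badly wrong. The conclusion is that the estimator is unspecified, subject to what the separate SAP says.

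**What to change.** In Section 11.4 and the SAP:

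1. Define Part B AUC(ss) as AUC0-24(ss).
2. Take Part B AUC out of the subject-level ANOVA. Estimate it per treatment and day from mean concentrations at the seven nominal times (sparse, or batch, noncompartmental analysis). The standard error must allow for repeated samples within a child. With complete data, form each child's weighted sum over the times of that child's set; the AUC is the Set 1 mean plus the Set 2 mean, and its variance is the sum of the two variances of those means. Prespecify one method for the 90% interval of the Test/Reference ratio. A population PK model that includes the Part A data is an alternative and keeps the geometric scale.
3. State that the three-concentration rule does not apply to this pooled AUC. Values set to zero can enter arithmetic means directly.
4. State that Day 14 and Day 21 are not combined, since for Test the Day 22 morning application is not rinsed off.

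The cost is wording and one program, with no change to sampling. There are downsides:

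- There would be no individual paediatric AUCs.
- Nominal times replace actual times, which needs an exception to the Section 11.4 sentence on sampling-time deviations (the sampling window is 15 minutes either way).
- The batch method gives a ratio of arithmetic means. For log-normal data the arithmetic mean exceeds the geometric by sqrt(1 + CV^2): 1.118 at CV 50% and 1.281 at CV 80%. If the arms had CVs of 80% and 50%, the ratio would shift by 1.281/1.118, about 15%.

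The last shift can exceed the 3% to 11% bias shown above, so the reason for the change is a defined quantity on a common interval, not a gain in precision.

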4 STUDY DESIGN

This will be a randomized, multiple-dose, laboratory-blinded, open-label, 2-arm, parallel-arm, multicenter study in subjects with moderate acne vulgaris.

Approximately 62 subjects will be randomized to receive either Test or Reference product, stratified by age (adult subjects: 17 years or older; pediatric subjects: 9 years to 16 years 11 months for the Test product and 12 years to 16 years 11 months for the Reference product) with approximately even distribution between males and females in each age stratum. The study will be conducted in two parts, Part A and Part B in a sequential manner. Based on full PK profiles generated for adult subjects in Part A, the sparse PK sampling design in pediatric subjects has been established in Part B. Part B (age 9 years to 16 years 11 months for DFD-03 and 12 years to 16 years 11 months for Reference) will enroll up to 38 subjects, which will include at least 6 subjects 9 to 11 years of age, and among those at least 2 subjects between 9 and 10 years of age. Target enrollment is 32 subjects, but up to 6 additional subjects may be enrolled to reach a minimum of 16 evaluable subjects, who have sparse samples collected on Day 14 and Day 21, randomized to the Test treatment.

PK profiling will be performed on Day 14 and on Day 21. Day 14 is selected as the earliest time point at which the steady state is expected to be achieved in subjects with moderate acne vulgaris, before any significant improvement in skin barrier occurs.

In Part A, 24 adult subjects will be enrolled such that 12 subjects each will be assigned to receive either Test or Reference treatment. In Part B, up to 38 subjects will be enrolled where approximately 26 subjects will receive Test treatment and 12 subjects will receive Reference treatment. Enrollment will continue until at least 16 evaluable subjects randomized to the Test treatment complete the study.

For 21 days, study product will be applied on the face, neck, upper chest, shoulders and upper back region, not exceeding 15% of the body surface area. The Test product will be applied twice daily, 12 hours apart (morning and evening; 42 consecutive doses), and the Reference product will be applied once daily in the evening (21 consecutive doses).

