11.1 Sample Size

Approximately 62 subjects will be enrolled in the study. Since the study is not aimed to meet the bioequivalence criteria, proper powering of the study is not required. The sample size chosen for the study attempts adequate representation of pediatric and adult population and was considered adequate to meet the study objectives.

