Descriptive statistics will be calculated for plasma concentrations at each individual time point and for all PK parameters. The individual plasma concentration/time profiles will be presented using the actual sampling times whereas the mean plasma concentration/time profiles will be presented using the theoretical sampling times. Concentration/time profiles will be presented on linear and semi-log scales.

Pharmacokinetic analyses will be generated using validated PK software (e.g. Phoenix[®] WinNonlin[®] Version 6.3 or higher and Phoenix[®] Connect[™] version 1.3.1 or higher).

A statistical plan will be prepared. Statistical analysis of all PK parameters will be based on a parametric analysis of variance (ANOVA) model. Two-sided 90% confidence intervals of the ratio of geometric least squares (LS) means will be presented from the natural log (ln)-transformed PK parameters ($C_{\max(ss)}$, $AUC_{0-24(ss)}$, $C_{\min(ss)}$) for Treatment 1 vs Treatment 2.

Achievement of steady state will be performed by treatment, using log-transformed $C_{\min(ss)}$ (at Days 12, 13 and 14 and 19, 20 and 21) in a mixed effect model through repeated-measure ANOVA or through other appropriate statistical methods.

Disease severity will be assessed between baseline and sampling days by paired t-test or any other appropriate statistical test and will be presented by treatment.

Descriptive statistics will be presented for safety parameters.

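### If ln-scale variances differ by arm, the default pooled-variance ANOVA in section 11.4 may move the Test/Reference 90% CIs off nominal coverage in the unbalanced Part B

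*Combined protocol and SAP*

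**What the plan says.** Section 11.4 names the model for the PK comparison, "Statistical analysis of all PK parameters will be based on a parametric analysis of variance (ANOVA) model", and the result to be reported: "Two-sided 90% confidence intervals of the ratio of geometric least squares (LS) means will be presented from the natural log (ln)-transformed PK parameters". It does not state the factors in the model, the residual variance structure, the degrees-of-freedom method, or whether Parts A and B are analysed separately or together. For steady state and disease severity, the same section allows another suitable method. For the Test/Reference CIs it does not. Section 11 announces a separate SAP, and section 11.4 says a statistical plan will be prepared. Neither is part of the documents.

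On allocation, section 4 says "In Part A, 24 adult subjects will be enrolled such that 12 subjects each will be assigned to receive either Test or Reference treatment". For Part B, "up to 38 subjects will be enrolled where approximately 26 subjects will receive Test treatment and 12 subjects will receive Reference treatment". It adds: "Target enrollment is 32 subjects, but up to 6 additional subjects may be enrolled to reach a minimum of 16 evaluable subjects" (on the Test treatment). Section 11.2.2 confirms the imbalance: "An unequal number of subjects per arm will be used".

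Section 6.2 sets out two very different ways of applying the products. Test goes on wetted skin twice daily and is rinsed off after about a minute, except for the last dose on Day 22. Reference goes on dry skin once daily and stays on for 12 hours. The Part B Test arm spans ages 9 to 16 and uses two amounts (about 5 g, or 4 g in the youngest group). The Reference arm spans ages 12 to 16 at about 5 g.

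**The concern.** In a parallel-arm comparison, the CI for the ratio rests entirely on between-subject variance. An ordinary ANOVA estimates one residual variance and weights each arm's variance by its degrees of freedom, so the larger arm dominates. The true variance of the difference in means divides each arm's variance by its own sample size, so the smaller arm dominates. The two agree when the arms are of equal size or the variances are equal. They disagree when both differ.

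Part B has unequal arms by plan, and the two modes of application give no reason to expect equal ln-scale variances. The 90% CI is the only between-treatment inference for the primary objective. What is at stake is therefore the stated precision of the main result: too optimistic if the small Reference arm is the more variable, too cautious if the large Test arm is.

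**Working it through.** **Inputs from the documents.** Nominal level 90%, two-sided, ln scale (11.4). Part A 12:12 and Part B at its ceiling 26:12 (section 4). Total 24 + 38 = 62, which agrees with section 11.1 ("Approximately 62 subjects will be enrolled in the study"). The Part B target of 32 gives 32 - 12 = 20 on Test, so 20:12 if Reference stays at 12 (an assumption). The minimum evaluable on Test is 16, so 16:12 on the same assumption. Both parts together would be 12 + 26 = 38 Test and 12 + 12 = 24 Reference, if they are ever combined.

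**Assumed input.** The documents give no ln-scale SD or CV for either arm. The ratio SD(Test)/SD(Reference) is varied from 0.5 to 2.

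**Formulas.** With arm sizes n1 (Test) and n2 (Reference) and ln-scale SDs s1 and s2:
- variance that the pooled ANOVA expects: [((n1 - 1)s1² + (n2 - 1)s2²)/(n1 + n2 - 2)] × (1/n1 + 1/n2)
- true variance of the difference: s1²/n1 + s2²/n2

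**Hand check at 26:12.**
- Reference twice as variable (s1 = 1, s2 = 2): pooled (25 × 1 + 11 × 4)/36 × (1/26 + 1/12) = 1.917 × 0.1218 = 0.233. True 1/26 + 4/12 = 0.372. Ratio 0.628, square root 0.79, so the standard error is about 21% too small.
- Test twice as variable (s1 = 2, s2 = 1): pooled (25 × 4 + 11 × 1)/36 × 0.1218 = 3.083 × 0.1218 = 0.376. True 4/26 + 1/12 = 0.237. Ratio 1.583, square root 1.26, so the standard error is about 26% too large.

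**Hand check at 12:12.** With s1 = 1 and s2 = 2, pooled (11 × 1 + 11 × 4)/22 × (2/12) = 2.5 × 0.1667 = 0.417. True 1/12 + 4/12 = 0.417. The two agree, which is why Part A is essentially unaffected.

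**Nominal level first.** Simulation used normal ln data, one value per subject and 1,000,000 draws per case. With equal SDs, the pooled interval has 90.0% coverage at 16:12, 20:12, 26:12 and 38:24. With equal SDs and a tenfold difference in geometric means, it has 89.9% at 26:12 and 90.0% at 38:24. So neither unequal numbers nor different mean exposure breaks coverage.

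**Coverage of the pooled 90% CI with unequal SDs:**

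| Test:Reference | SD ratio 0.5 | 0.67 | 1.5 | 2 |
|---|---|---|---|---|
| 26:12 (Part B ceiling) | 80.7% | 84.5% | 94.1% | 95.8% |
| 20:12 (Part B target) | 83.8% | 86.4% | 92.8% | 94.1% |
| 16:12 (Part B minimum on Test) | 86.5% | 87.9% | 91.6% | 92.3% |
| 38:24 (only if parts combined) | 84.6% | 86.8% | 92.7% | 93.9% |

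Part A at 12:12 stays between 89.6% and 90.0%. A combined model with treatment and part as factors (40,000 draws) gives 84.7, 86.8, 92.3 and 93.8%, much like the simple 38:24 row.

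**In CV terms.** With SD = √ln(1 + CV²), a CV of 50% is an SD of 0.472 and a CV of 80% is 0.703, a ratio of 0.67. At 26:12, Test 50% with Reference 80% gives 84.6% coverage, and the reverse gives 94.1%.

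**With arm-specific variances** (Welch/Satterthwaite), coverage is 89.9% to 90.1% in every unbalanced case. If the variances are equal, the mean half-width at 26:12 with SD 0.6 is 0.356 ln units against 0.351 pooled: 0.356/0.351 = 1.014, or 1.4% wider.

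**The case against.** A reader might infer that, because the arms are unequal and receive very different exposures, the CIs will not have 90% coverage. The documents do not support that. A difference in exposure level is a location shift on the ln scale, and coverage is 90% at every allocation when the ln-scale SDs are equal. Only unequal variances matter, and the documents report none.

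The rest of the case against has weight too:
- **Direction.** The heterogeneity that the protocol does describe (two amounts, wider age range) lies mainly in the larger Test arm. If that dominates, the intervals are too wide rather than too narrow. The direction is open.
- **Allocation.** 26:12 is the enrolment ceiling. At 16:12 with a 1.5-fold SD difference, coverage is only about two points off (87.9% or 91.6%).
- **Combining parts.** Nothing says that Parts A and B will be combined, so the 38:24 figures are conditional.
- **Unseen SAP.** Pooled variance is the default reading of ANOVA, not a stated choice, and the separate SAP could specify otherwise. However, the protocol has already named the model and offers no alternative for this comparison.
- **Stakes.** Section 11.1 says the study does not aim to meet bioequivalence criteria, and no acceptance limits are given. No pass/fail error rate is affected.
- **Simulation.** It assumes one normal ln value per subject. In Part B each subject gives 3 or 4 samples per PK day, values below the quantitation limit are set to zero, and AUC is dropped when fewer than three consecutive values are measurable. The figures, including the 90% under the remedy, are therefore indicative for Part B.

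These points limit the claim and its severity. They do not remove the sensitivity of a pooled interval in an unbalanced parallel comparison.

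**Conclusion.** The point holds in conditional form. As section 11.4 reads by default, the Part B CIs may depart from 90% coverage if ln-scale variances differ by arm. The same applies to a combined analysis if one is done. For SD ratios of 1.5 to 2 in either direction, the departure runs from about nine points low to six points high at 26:12, and is smaller at 20:12 and 16:12. Part A is essentially unaffected. The size rests on assumed SD ratios, on Reference staying at 12 and on normal ln data. Unequal variances are plausible from the two modes of application but are not established. Since the CI is the only between-treatment inference for the primary objective but feeds no bioequivalence decision, this is a cheap improvement to the reported precision and not a must-fix.

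**What to change.** In section 11.4 and in the SAP, state that the ln-transformed PK parameters are fitted with a separate residual variance for each treatment and Satterthwaite degrees of freedom (for example PROC MIXED with REPEATED / GROUP=treatment). Take the ratio and its 90% CI from that model for every parameter and day. State also whether Parts A and B are analysed separately or combined.

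Fix this before Part B concentrations are seen. Section 7.5 says the Part A PK assessment is already done, so the sponsor can look at the adult SD ratio now as background. It need not drive the choice, because the remedy costs so little.

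The cost is a line or two in the SAP and, if the variances are equal, a CI about 1-1.5% wider.
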